#### **6.8.6.      Electrocardiograms and Echocardiogram**

The frequency and percentage of patients with values meeting the potentially clinically significant abnormality criteria (defined in [Appendix Table 5](#)) at any time point will be summarized by Analysis Period and treatment group as defined in Section [5.1](#) for both ECGs and ECHOs. The number of potentially clinically significant abnormalities will also be presented.

Baseline value, highest/largest absolute change/largest change (ECGs only) and last observation and the corresponding change from Baseline will be summarized by treatment group. The largest change will be summarized for QTcF, QRS and PR intervals, the highest value for QT and largest absolute change for heart rate. If the largest absolute change from Baseline is occurs in both directions equally then the higher value will be summarized. Only results that occurred within 28 days of the last dose of study drug, or before initiation of a new study drug will be included.

All patient-level values for ECG and ECHO variables will be displayed in a data listing. In addition, values meeting the potentially clinically significant criteria will be presented in a data listing. Treatment-emergent abnormalities will be indicated.

CCI

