6. STUDY OBJECTIVES

6.1. Primary Objective

- To evaluate the safety and tolerability of 4 escalating IV doses (4, 10, 20, and 30 mg/kg) of SRP-4045 administered once weekly for at least 2 weeks per dose level as compared to placebo.

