7.3. Study Endpoints

The following study endpoints will be evaluated in this study. Descriptions of all study assessments and procedures are provided in Section 10.

The primary endpoint is assessment of the safety of SRP-4045 during the double-blind dose-titration period according to the following:

- Incidence of AEs

- Incidence of clinical laboratory abnormalities (hematology, chemistry, coagulation, urinalysis)
- Incidence of abnormalities in vital signs and physical examinations
- Clinically significant worsening of ECGs and ECHO

The secondary endpoint is to determine the PK profile of SRP-4045 during the double-blind dose-titration period:

[figure not shown]
- Maximum plasma concentration (C_{max})
- Time to maximum plasma concentration (T_{max})
- Area under the plasma concentration-curve (AUC)
- Apparent volume of distribution at steady state (V_{ss})
- Elimination half-life ($t_{1/2}$)
- Total clearance (CL)
- Mean residence time (MRT)
- Urinary clearance (CL_R)

CCI

[figure not shown]

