#### 4.4.1. Safety Endpoints

The safety and tolerability of casimersen doses at 4, 10, 20, and 30 mg/kg for at least 2 weeks per dose for double-blind and open-label period will be assessed through a review and evaluation of the following:

- incidence of treatment-emergent adverse events (TEAEs)
- incidence of clinical laboratory abnormalities (hematology, chemistry, coagulation, urinalysis)
- incidence of abnormalities in vital signs and physical examinations
- incidence of abnormalities on electrocardiograms (ECGs) and echocardiograms/echocardiography (ECHOs)

[figure not shown]

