## **6.8. Safety Analyses**

Safety analyses by Analysis period and treatment groups described in Section 5.1 (double-blind period and casimersen period) will include summaries of the following:

- the type, frequency, severity, timing, and relationship to the study drug of AEs, SAEs, and discontinuations due to AEs. Adverse events will be coded using the Medical Dictionary for Regulatory Activities (MedDRA 17.1 and will be reported by primary system organ class (SOC) and preferred term (PT)).
- safety laboratory testing including hematology, coagulation, serum chemistry, and urinalysis
- vital signs
- physical examinations
- 12-lead ECGs
- ECHOs

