#### **6.8.4. Clinical Laboratory Evaluation**

A shift table will present the number and percentage of patients in each cell resulting from cross-tabulating the status (low, normal, and high) of the highest/lowest post-baseline value versus that of the Baseline for each laboratory test, if applicable, by analysis period and treatment group as defined in Section 5.1. If a specific test can have both a significant low and high, then a shift table will be generated for each direction. The percentage will be based on the total number of patients in the Safety Set. A status of missing may be added, if necessary. This analysis will be repeated for last post-baseline result.

Only the highest value will be summarized for alanine aminotransferase (ALT), alkaline phosphatase, amylase, aspartate aminotransferase (AST), C-reactive protein, creatine kinase, creatinine, cystatin C, gamma glutamyl transferase (GGT), lactate dehydrogenase (LDH), total bilirubin, uric acid, absolute basophils, absolute eosinophils, basophil percent, eosinophil percent, activated partial thromboplastin time, international normalized ratio, prothrombin time, and urine KIM-1, and urine protein. Only the lowest value will be summarized for albumin, and platelets. Both the highest and lowest values will be summarized for blood urea nitrogen (BUN), calcium, chloride, glucose, potassium, sodium, absolute lymphocytes, absolute monocytes, absolute neutrophils, hematocrit, hemoglobin, lymphocyte percent, monocyte percent, neutrophils percent, white blood cell (WBC) count, and urine pH and specific gravity.

The frequency and percentage of patients meeting the potentially clinically significant abnormality criteria (defined in [Appendix Table 1](#), [Appendix Table 2](#), [Appendix Table 3](#)) at any time point post-baseline will be summarized by Analysis Period and treatment group. Additionally, the total number of potentially clinically significant abnormalities will be summarized.

Baseline value, highest/lowest value and last observation and the corresponding change from Baseline will be summarized by Analysis Period and treatment group.

All patient-level clinical laboratory values will be displayed in data listings. In addition, values meeting the potentially clinically significant abnormalities criteria will be presented in data listings. Treatment-emergent abnormalities will be indicated in the listing.

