#### **6.8.5. Vital Signs and Other Physical Findings**

The frequency and percentage of patients meeting any of the potentially clinically significant abnormality criteria (defined in [Appendix Table 4](#)) at any time point post-baseline will be summarized by Analysis Period and treatment group as defined in Section 5.1. Additionally, the total number of potentially clinically significant abnormalities will be summarized.

Baseline value, highest/largest absolute change and last observation and the corresponding change from Baseline will be summarized by analysis period and treatment group. The largest absolute change from Baseline will be summarized for systolic blood pressure, diastolic blood pressure, and respiratory rate, and the highest value for pulse and temperature. If the largest absolute change from Baseline occurs in

both directions equally, then the higher value will be summarized. The highest/largest absolute change value will not be summarized for height, weight, BMI, ulnar length, or calculated height. Only results that occurred within 28 days of the last dose of study drug, or before initiation of a new study drug will be included.

Vital signs will be listed for all patients. In addition, values meeting the potentially clinically significant criteria will be presented in a data listing. Treatment-emergent abnormalities will be indicated. Height and weight will also be listed.

[figure not shown]

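### Worsening on ECHO is part of the primary safety endpoint, but the SAP counts ECHO values below a fixed level, so a patient with stable low LVEF at entry is counted without having worsened

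*SAP*

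**What the plan says.** Protocol 7.3 lists four primary safety components for the double-blind dose-titration period. For laboratory tests, and for vital signs and physical examinations, the component is an incidence of abnormalities. For cardiac tests it is different: "Clinically significant worsening of ECGs and ECHO". Protocol 6.1 sets the comparison, with the doses "administered once weekly for at least 2 weeks per dose level as compared to placebo".

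SAP 4.4.1 restates the cardiac component as "incidence of abnormalities on electrocardiograms (ECGs) and echocardiograms/echocardiography (ECHOs". SAP 6.8.6 then counts patients meeting the Appendix Table 5 criteria "at any time point will be summarized by Analysis Period and treatment group as defined in Section" 5.1. The matching sentence for laboratory tests (SAP 6.8.4) reads "at any time point post-baseline will be summarized by Analysis Period and treatment group", and the one for vital signs (SAP 6.8.5) reads "at any time point post-baseline will be summarized by Analysis Period and treatment group as defined in Section 5.1".

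The two ECHO rows of Appendix Table 5 are fixed levels for all ages: LVEF below 55% and fractional shortening below 29%. Neither has a change condition. Protocol 8.2, criterion 8, excludes LVEF below 40% on the Screening ECHO.

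SAP 6.8.6 also plans a summary of the Baseline value, "highest/largest absolute change/largest change (ECGs only) and last observation and the corresponding change from Baseline will be summarized by treatment group". SAP 6.8 applies the safety analyses as "described in Section 5.1 (double-blind period and casimersen period) will include summaries of the following".

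**The concern.** The protocol asks who got worse. The SAP count asks who is below a level. In this population the two can differ, because entry is open to patients already below the counting level. Such a patient enters the count whatever happens on treatment, and a patient whose LVEF falls but stays at or above 55% never does.

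With arms of 8 and 4, one patient moves the displayed rate a long way. The casimersen and placebo columns for a primary safety component could therefore differ because of cardiac status at entry, in either direction, with nobody having changed.

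**Working it through.** There is no figure in the plan to reproduce: SAP 4.2 rests the sample size on qualitative considerations. The check sets the rules side by side and then works out the size.

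**1. Gap between entry and counting levels.** Entry allows LVEF of 40% or more (Protocol 8.2); the count takes LVEF below 55% (Appendix Table 5). The gap is 55 - 40 = 15 LVEF points.

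**2. The rule applied to example patients** (Baseline to post-baseline LVEF, %):

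| Patient | Counted under SAP 6.8.6 | Counted if only post-baseline values are used | Below 55% post-baseline but not at Baseline |
|---|---|---|---|
| 50 to 50 | yes | yes | no |
| 45 to 45 | yes | yes | no |
| 50 to 53 | yes | yes | no |
| 50 to 58 | only if Screening is inside the period | no | no |
| 60 to 54 | yes | yes | yes |
| 70 to 56 | no | no | no |

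Limiting the count to post-baseline values removes only the fourth case. Stable low LVEF stays in. The 70-to-56 patient is missed by all three counts and is seen only through change from Baseline.

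**3. Whether the Screening ECHO is inside the count.** SAP 5.1 defines the Double-Blind Period by its end (before the first open-label dose) and states no start. The 28-day rule in 6.8.6 sets no start at Baseline either. On that wording the Screening value can be counted. The casimersen groups in 5.1, however, are defined from Week 1, which allows the opposite reading. Steps 1, 4 and 5 do not depend on which is right.

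**4. Size per patient.** 1/8 = 12.5 points on casimersen; 1/4 = 25 points on placebo.

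Suppose k of the 12 patients enter at 40-54%, nobody changes and nobody else meets a criterion. No stratification is stated, so the chance that c of the k are on casimersen is C(8,c) × C(4,k-c) / C(12,k).

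- k = 1: 12.5% v 0% with probability 8/12 = 0.667; 0% v 25% with probability 4/12 = 0.333. Mean absolute difference = 0.667 × 12.5 + 0.333 × 25 = 16.7 points.
- k = 2: 25% v 0% with probability 28/66 = 0.424; 12.5% v 25% with probability 32/66 = 0.485; 0% v 50% with probability 6/66 = 0.091. Mean absolute difference = 0.424 × 25 + 0.485 × 12.5 + 0.091 × 50 = 21.2 points.

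A count of patients new since Baseline gives 0% v 0% in each case. That follows directly from assuming that nobody changes; the calculation shows only how much entry status alone can put into the table.

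**5. How likely it is that the issue arises.** The documents do not give the share f entering at 40-54%, so f is assumed. The chance of at least one among 12 is 1 - (1 - f)^12:

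- f = 5%: 0.46
- f = 10%: 0.72
- f = 20%: 0.93

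**6. What the change summary covers.** ECHO is done at Screening, Week 12 and then every 24 weeks (Protocol 7.1). Blinded treatment runs to about 4 weeks after the last enrolled patient's 12 weeks (Protocol 9.9.2), so about 12 + 4 = 16 weeks for that patient. Week 12 is then normally the only post-baseline double-blind ECHO, and so the last observation. The exception is a patient who starts about 36 - 16 = 20 weeks or more before the last one and is still blinded at Week 36.

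**The case against.** **The other summaries already separate low entry from a fall.** This largely stands. SAP 6.8.6 summarises Baseline, last observation and change, and SAP 5.1 includes the minimum and maximum. In arms of 8 and 4, the Baseline minimum shows whether anyone entered below 55%, and the minimum change shows the largest fall at last observation. Every value is listed. A reader might infer that a fall on ECHO cannot be told apart from low entry LVEF; the documents do not support that. What these outputs do not give is the number of patients per arm whose ECHO worsened.

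**Later ECHOs do not bear on the primary endpoint.** This stands. The extreme-change summary is for ECGs only, and a reader might infer that unsummarised later ECHOs weaken the comparison with placebo. They are mostly open-label, outside the primary endpoint and without a concurrent placebo arm.

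**Fixed levels are the SAP's general convention.** True: many laboratory and vital-sign criteria are fixed levels too. But for those the protocol asks for abnormalities. Only for ECG and ECHO does it ask for worsening. For ECGs, Appendix Table 5 at least has a QTcF increase criterion.

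**Worsening has an adverse-event route.** It does. The investigator judges clinical significance (Protocol 10.3.5.2), a Screening abnormality that worsens can be an AE (11.2.1), and cardiac events are tabulated (SAP 6.8.3). This captures worsening that becomes an AE, not every ECHO decline, and SAP 6.8.6 specifies no table of the investigator's judgement.

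**Other inferences to avoid.** The treatment-emergent mark in 6.8.6 is described for data listings, and the visible part of SAP 5.8 defines such abnormalities only for laboratory tests. No promise of an ECHO shift table is broken, since Protocol 12.4.7 covers only select parameters. Nor can it be said that SAP 7.1 leaves the changed endpoint undeclared, because part of that list is redacted. Inclusion criterion 3 and exclusion criterion 11 set no numerical limit on how many patients may enter at 40-54%.

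**Conclusion.** The point holds. The SAP's ECHO count does not measure the worsening that the protocol names as a primary safety component. A stable LVEF of 40-54% is counted, at 12.5 points per casimersen patient or 25 per placebo patient, and a fall that stays at or above 55% is not. That much follows from the two documents without assumption. How often it happens rests on an assumed share entering low.

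A reader might go further and conclude that the Screening ECHO is certainly counted, so that a patient who improves from 50% to 58% appears as abnormal. The wording permits this but does not settle it.

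The consequence is limited. The analysis is descriptive, with 12 patients, full listings and a change-from-Baseline summary that normally covers the single post-baseline double-blind ECHO. The change is still worth making: a primary component should have a table that answers its own question.

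**What to change.** - In SAP 6.8.6, limit the ECG and ECHO counts to post-baseline values, as 6.8.4 and 6.8.5 do. Keep the Appendix Table 5 row for Screening QTcF above 450 msec as a separate baseline summary.
- Because that alone still counts stable low LVEF, also report by arm the patients who meet an ECHO criterion post-baseline but did not at Baseline, or a baseline-to-worst shift table for LVEF and fractional shortening. Put change from Baseline beside it. Otherwise further decline in a patient already below the level, or a fall that stays above it, is missed, and a patient just above 55% who crosses through measurement variation looks like a clear case.
- Extend the treatment-emergent abnormality definition in SAP 5.8 to ECG and ECHO.
- Add the lowest post-baseline LVEF and fractional shortening with change from Baseline. This is useful mainly for the Casimersen Period, which holds several ECHOs.
- Any fixed change category is for the sponsor to set before unblinding.

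The cost is SAP wording and one sparse descriptive table. No new ECHOs or data are needed.

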#### **6.10.      Pharmacokinetic Analyses**

The PK of casimersen will be determined from plasma and urine samples collected serially following the first weekly doses on Weeks 1, 3, 5, and 7 and 60 and from plasma samples collected at Weeks 12, 24, 36, 48, 72, 84, 96, 108, 120, 132. Individual plasma levels of casimersen will be listed with the corresponding time related to study drug product administration (actual time), and summary statistics will be generated by per-protocol time of collection (nominal time). Pharmacokinetic parameters for casimersen will be calculated using noncompartmental analysis. Actual sampling times will be used in all final PK analyses. Per-protocol times will be used to calculate mean plasma

concentrations for graphical displays. The PK parameters that will be determined include:  $C_{max}$ ,  $t_{max}$ , AUC,  $V_{ss}$ ,  $t_{1/2}$ , CL, MRT and CLR.

Pharmacokinetic data will also be analyzed based on [REDACTED] using plasma concentration data and appropriate demographic and baseline characteristics.

The details of PK analyses will be described in a separate PK and/or [REDACTED] SAP.

[REDACTED]

CCI

When and where warranted, PK parameters (eg, AUC) and selected safety and efficacy results may be further summarized (stratified) by antibody status (antibody negative vs. positive) and treatment group.

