Eligible patients who have out-of-frame deletions that may be corrected by skipping exon 45 will be randomized to receive once-weekly IV infusions of SRP-4045 or placebo.	

NAME OF COMPANY	NAME OF FINISHED PRODUCT
Sarepta Therapeutics, Inc. [name] [contact]	SRP-4045 Injection
NAME OF ACTIVE INGREDIENT	
SRP-4045	

Double-Blind Dose Titration with Open-Label Extension (144 weeks)

Dosing

Twelve patients will be randomized (2:1) in double-blind fashion to receive SRP-4045 (n=8) or placebo (n=4). Patients will receive a once-weekly IV infusion of SRP-4045 or placebo at escalating dose levels, each for at least 2 weeks: 4 mg/kg at Weeks 1-2; 10 mg/kg at Weeks 3-4; 20 mg/kg at Weeks 5-6; and 30 mg/kg beginning at Week 7. During the dose titration period of the study, dosing will be interrupted or halted if specific predefined stopping criteria are met, or if interruption is otherwise warranted at the discretion of the Sponsor or Investigator. Once the last patient has received 2 infusions at 30 mg/kg (Week 8), an independent Data Safety Monitoring Board (DSMB) will review cumulative safety data. Review by the DSMB is necessary for advising the Sponsor about whether the safety data allow for longer-term dosing with SRP-4045. Patients will continue to receive their randomized treatment (SRP-4045 or placebo) in a blinded fashion until the DSMB review is complete. Based on the results of this review, the Sponsor will determine whether to roll over the patients into the open-label extension period. During the open-label extension, patients will receive SRP-4045 at 30 mg/kg (or the highest tolerated dose as determined during the dose titration) administered weekly.

Assessments

Patients will undergo routine safety evaluations. Adverse events (AEs) and concomitant medications will be monitored and documented continually over the course of the study.

CCI

Plasma samples for serial PK determination will be collected at Baseline/Week 1 and Weeks 3, 5, 7, and 60. Urine samples for serial PK determination will be collected at Baseline/Week 1 and Weeks 3, 5, 7, and 12.

In addition to serial PK, standard population PK parameters will be estimated from additional plasma samples taken over the course of 144 weeks.

CCI

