- ^g Randomization (8 SRP-4045 + 4 placebo) will occur at Baseline/Week 1 after confirming all eligibility criteria prior to first dose.
- ^h 12-lead ECGs and ECHOs will be performed at a consistent time of day throughout the study.
- ⁱ Safety laboratory assessments must be performed within 2 weeks prior to the Baseline/Week 1 visit, and results must be reviewed prior to dosing. If Screening safety laboratory samples were collected more than 2 weeks prior to the Baseline/Week 1 visit, samples must be collected again and results must be reviewed before patients may be dosed at Baseline/Week 1.

CCI

- ^j Serial plasma PK sampling will be performed during the double-blind dose-titration period at Baseline/Week 1 and Weeks 3, 5, and 7 at the following time points at the first weekly dose for each dose level: immediately pre-infusion, approximately 5 to 10 minutes after completion of infusion, and at approximately 1, 1.5, 2, 4, 6, 8, 12, 16, and 24 hours after completion of infusion. At Weeks 1, 3, 5, 7, and 12, urine for PK sampling will be collected, on a cumulative basis, during the following time intervals based on start of infusion: 0 to 4, 4 to 8, 8 to 12, and 12 to 24 hours. In addition, at Week 7, urine will also be collected 24 to 36 hours after the start of infusion. Patients will be asked to void their bladders prior to the start infusion.

CCI

- ^l Randomized patients will be dose-escalated every 2 weeks to receive weekly infusions of SRP-4045 or placebo at: 4 mg/kg/week (Weeks 1-2), 10 mg/kg/week (Weeks 3-4), 20 mg/kg/week (Weeks 5-6), and 30 mg/kg (Week 7 to DSMB safety review). The initial 4 patients will be staggered with a minimum of 3 days between administrations of the initial doses to each of these patients. Infusions are to be given according to instructions in the Pharmacy Manual. Patients are to be closely monitored for at least 1 hour following the completion of all infusions.

- ^m DSMB safety data evaluation begins once the last patient has received 2 infusions at 30 mg/kg (Week 8). Patients shall continue to receive double-blind treatment (SRP-4045 30 mg/kg or placebo) until the DSMB completes its review. Based on the results of this review, the Sponsor will determine whether to roll over patients into the open-label extension period.

Table 2: Schedule of Events: Double-Blind Dose Titration with Open-Label Extension, continued

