10.5. Pharmacokinetic Assessments

10.5.1. Blood Sample Collection

Blood collection for serial PK determination will occur at the time points specified in the schedule of events (Table 2): immediately pre-infusion, at approximately 5 to 10 minutes after the end of infusion, and then at approximately 1, 1.5, 2, 4, 6, 8, 12, 16, and 24 hours after the end of infusion at Baseline/Week 1 and Weeks 3, 5, 7, and 60.

CCI

Blood collection for PK must be drawn from the arm contralateral to the treatment infusion. Pharmacokinetic samples may not be drawn from a patient's implanted venous port if treatment is infused via the port.

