10.5.2. Urine Sample Collection

Urine for PK determination will be collected on a cumulative basis, during the following time intervals at the time points specified in the schedule of events (Table 2) based on start time of study drug infusion: 0 to 4 hours, 4 to 8 hours, 8 to 12 hours, 12 to 24 hours, and additionally at Week 7, 24-36 hours. Patients will be asked to void their bladder prior to start of study drug infusion.

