12.4.8. Pharmacokinetic Analyses

The PK profile of SRP-4045 will be determined from multiple plasma samples collected serially before and after the first weekly infusion at each dose level in the dose titration phase at Weeks 1, 3, 5, and 7 and also at Week 60 in the open-label extension. In addition, multiple urine samples will be collected serially after the first infusion at each dose level in the dose titration phase and at Week 12. Individual plasma levels of SRP-4045 will be listed with the corresponding time related to investigational drug product administration and summary statistics will be generated by per-protocol time of collection. Pharmacokinetic parameters for SRP-4045 will be calculated using non-compartmental analysis. Actual sampling times will be used in all final PK analyses. Per-protocol times will be used to calculate mean plasma concentrations for graphical displays. The PK parameters that will be determined only for Weeks 1, 3, 5, 7, and 60 include:

- C_{max}
- T_{max}
- AUC
- V_{ss}

- $t_{1/2}$
- CL
- MRT
- CL_R

CCI

Available patient characteristics (demographics, laboratory variables, genotypes, concomitant medications, etc) will be tested as potential covariates affecting PK parameters.

CCI

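### Does listing urinary clearance (CL_R) at Week 60, where the visible protocol schedules no PK urine, call for a change to the plan?

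*SAP*

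**What the plan says.** Protocol 12.4.8 fixes the visits for the non-compartmental parameters: "The PK parameters that will be determined only for Weeks 1, 3, 5, 7, and 60 include" eight items, the last of which is CL_R. On urine, the same section says that "multiple urine samples will be collected serially after the first infusion at each dose level in the dose titration phase and at Week 12".

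The rest of the protocol gives the same urine visits. The synopsis has "Urine samples for serial PK determination will be collected at Baseline/Week 1 and Weeks 3, 5, 7, and 12", section 7.1 repeats this, and the PK footnote to Table 2 has "At Weeks 1, 3, 5, 7, and 12, urine for PK sampling will be collected, on a cumulative basis". Section 10.5.2 refers to Table 2 for the visits and gives the collection intervals: "0 to 4 hours, 4 to 8 hours, 8 to 12 hours, 12 to 24 hours, and additionally at Week 7, 24-36 hours". Serial blood sampling under section 10.5.1 runs to "24 hours after the end of infusion at Baseline/Week 1 and Weeks 3, 5, 7, and 60".

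SAP 6.10 bases the PK analysis on "plasma and urine samples collected serially following the first weekly doses on Weeks 1, 3, 5, and 7 and 60". It then names a second group of visits, Week 12 among them, for which it mentions plasma alone: "and from plasma samples collected at Weeks 12, 24, 36, 48, 72, 84, 96, 108, 120, 132". SAP 4.4.2 lists CL_R for both study periods, but its sentence on Week 60 refers only to serum parameters. Protocol 7.3 confines the secondary PK endpoint to the double-blind dose-titration period.

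**The concern.** Read together, these sections promise an output without an input. Renal clearance cannot be calculated without urine, and on the protocol's visible schedule nobody collects PK urine at Week 60. The SAP then says that urine is collected at that visit and mentions Week 12 only under plasma, so the two documents seem to disagree about what was sampled. The visible entries in SAP 7.1 record no such change, although Protocol 12.1 says departures from the protocol's analyses will be noted in the SAP.

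At stake would be the only open-label value of CL_R. Protocol 9.8.1 expects the most likely drug-related adverse events to involve renal function, so a reader might look for long-term renal clearance of the drug and find an empty table cell without explanation.

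**Working it through.** The plan states no figure to reproduce, so the check compares visits and inputs.

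**What CL_R needs.** Over a common interval from 0 to t, CL_R = (amount excreted in urine) / (plasma AUC). Total clearance, CL = dose / AUC, needs no urine.

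**Visits, side by side.**

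| Item | Source | Weeks |
|---|---|---|
| CL_R listed | Protocol 12.4.8 | 1, 3, 5, 7, 60 |
| Serial plasma | Protocol synopsis, 7.1, 10.5.1, 12.4.8 | 1, 3, 5, 7, 60 |
| PK urine | Protocol synopsis, 7.1, Table 2 footnote, 12.4.8 | 1, 3, 5, 7, 12 |
| Serial plasma and urine as analysis inputs | SAP 6.10 | 1, 3, 5, 7, 60 |

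- CL_R listed and urine scheduled in the protocol: Weeks 1, 3, 5 and 7, that is 4 of 5.
- CL_R listed without urine scheduled in the protocol: Week 60.
- Urine scheduled in the protocol without a listed parameter: Week 12, which has no serial plasma either.

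**Samples per patient.**

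- Urine intervals at Weeks 1, 3, 5 and 7: 4 + 4 + 4 + 5 = 17.
- Urine intervals at Week 12: 4, giving 17 + 4 = 21 in all.
- Urine intervals visible in the protocol for Week 60: 0.
- Serial plasma samples at Week 60: pre-infusion, 5 to 10 minutes, and 1, 1.5, 2, 4, 6, 8, 12, 16 and 24 hours, that is 2 + 9 = 11.

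**Is Week 12 a conflict?** No. SAP 6.10 says which samples the PK analysis draws on; it is not a collection schedule. Protocol 12.4.8 lists no parameter for Week 12, so an analysis sentence that leaves out the Week 12 urine is consistent with it. Only Week 60 is a true mismatch.

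**What happens at analysis.** There are two cases.

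1. No urine was collected at Week 60. The numerator is missing and CL_R cannot be formed. Protocol 12.1 rules out imputation unless an analysis explicitly provides for it. SAP 5.2.2 imputes only laboratory values, by its quantitation-limit rule, and dates. The Week 60 entry is blank. The other seven parameters (Cmax, Tmax, AUC, Vss, half-life, CL and MRT) come from plasma and are unaffected.
2. Urine was collected at Week 60. CL_R is calculated from it, as SAP 6.10 describes.

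The data settle which case applies. Neither leaves the analyst a choice that could move a result, and CL_R at Weeks 1, 3, 5 and 7, one visit per dose level, is the same in both.

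**The case for a change.** The best case for acting is that the correction is cheap and the statement is wrong somewhere. Protocol 12.4.8 conflicts with its own urine sentence. Text edits would add no procedure and no patient burden. They would also make plain that, without Week 60 urine, CL_R on drug comes from at most the 8 patients randomized to casimersen, because the 4 placebo patients first receive drug in the open-label period. The separate PK SAP may add detail, but it cannot correct a sampling statement in this SAP.

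The mismatch stands, and so does the limit of 8 patients. The rest carries less weight. Restricting CL_R to Weeks 1, 3, 5 and 7 presumes that the protocol is right and the SAP wrong. The SAP was written with the study under way: it is based on Protocol Amendment 3, and section 4.5.1 describes periodic safety reviews in the past tense. Its Week 60 urine could be a slip or a record of what was done, and the documents do not say which. SAP 4.4.2, by speaking of serum parameters at Week 60, can already be read as leaving CL_R out.

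The renal argument does not depend on CL_R. Protocol 9.8.1 assigns renal safety monitoring to urine protein, serum creatinine, BUN, cystatin C and KIM-1. These belong to the safety laboratory panel, which continues through the open-label period. The only version of the change that would yield new information is collecting urine at Week 60, and on the protocol's schedule that is an added procedure for a visit outside the secondary endpoint.

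**Conclusion.** No change to the plan follows. This is a clerical inconsistency about one descriptive parameter (CL_R) at one open-label visit (Week 60), and those doing the PK analysis will resolve it from the samples they have. A text correction would at most remove an output that could not be computed anyway. It would leave unchanged the double-blind secondary PK endpoint, CL_R at all four dose levels and the Week 60 plasma parameters. Aligning the wording if the documents are revised for other reasons would be tidy, but nothing depends on it.

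The conclusion rests on two assumptions. First, the visible urine lists are taken as complete. They read that way, but there is blacked-out text near the PK footnotes and in Protocol 7.1, Protocol 10.5.1 and SAP 7.1, so Week 60 urine cannot be ruled out. Second, the separate PK SAP, to which SAP 6.10 leaves the details, is assumed not to impute or otherwise substitute for missing urine. If Week 60 urine is in fact scheduled, the mismatch disappears and the conclusion is the same.
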